11.0 Statistical Considerations

Power calculation.

In a prior cluster-randomized cluster-crossover trial in the same ICU,⁵¹ 880 mechanically ventilated adults were enrolled per year (73.3 per month), with a median of 22 VFDs [IQR 0-25 VFDs] and an intra-cluster intra-period correlation of 0.01. During the planned 36-month PILOT trial, we estimate 2,640 mechanically ventilated adults will be admitted to the study ICU, of whom 390 will be enrolled during washout periods and excluded from the primary analysis and 2,250 will be included in the primary analysis. With a total enrollment of 2,250 patients, a standard deviation in the primary outcome of VFDs of 11.4 days, and a two-sided alpha of 0.05, ***the PILOT trial will have 92 percent statistical power to detect an absolute difference between groups in VFDs of 2.0 days*** (similar to the numerical difference in VFDs between SpO₂ target groups reported in prior studies^{29,30}).

Primary analysis of the Primary Outcome.

The primary analysis will be an intention-to-treat comparison of the primary outcome of VFDs between the higher, intermediate, and lower SpO₂ target groups among all patients enrolled in the trial except [1] those admitted during one of the 7-day washout periods and [2] those with a laboratory-confirmed diagnosis of Coronavirus disease 2019 (COVID-19). We will use a proportional odds model with independent covariates of group assignment (higher, intermediate, or lower SpO₂ target) and time. Time (in days) will be treated as a continuous variable with values ranging from 1 (first day of enrollment) to 1,097 (final day of enrollment) and will be analyzed using restricted cubic splines with multiple knots to allow for non-linearity resulting from seasonality or secular trends. For the purposes of declaring a statistically significant

difference between groups in the primary endpoint, we will consider the conditional effect from the proportional odds model and a two-sided P value of 0.05. In addition to the overall comparison of the three study groups, we will perform pair-wise comparisons between the lower and intermediate groups, lower and higher groups, and intermediate and higher groups using the same statistical approach.

Sensitivity Analyses of the Primary Outcome

- We will repeat the primary analysis using alternative statistical approaches to comparing the VFDs outcome between groups. These statistical approaches will include:
 - zero-inflated Poisson regression;

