 - zero-inflated negative binomial regression;
 - global rank scale analysis (see Supplementary Appendix); and
 - Fine and Gray competing risk regression in which extubation from invasive mechanical ventilation is the event of interest and mortality is a competing event.
- We will repeat the primary analysis with adjustment for pre-specified baseline covariates.
- We will repeat the primary analysis replacing the continuous covariate of time with a categorical covariate of season defined as: winter (January, February, March); spring (April, May, June); summer (July, August, September); and fall (October, November, December).
- We will repeat the primary analysis among all patients enrolled in the trial, including [1] patients initiated on invasive mechanical ventilation in a study location during one of the pre-specified 7-day washout periods and [2] patients with a diagnosis of COVID-19 (estimated sample size of 3,000 patients).

Analysis of Effect Modification for the Primary Outcome.

We will examine whether pre-specified baseline variables modify the effect of study group on the primary outcome using formal tests of statistical interaction in a proportional odds model. Independent variables will include study group assignment, the potential effect modifier of interest, and the interaction between the two (e.g., study group * presence of sepsis or septic shock) and time. Significance will be determined by the P value for the interaction term, with values less than 0.10 considered to suggest a potential interaction and values less than 0.05 considered to confirm an interaction.

We will examine whether the following baseline variables modify the effect of study group on the primary outcome:

- Age (continuous variable);
- Race and ethnicity (Hispanic, Non-Hispanic Black, Non-Hispanic White, Other);
- Source of admission to the ICU (ED, hospital ward, another ICU in the study hospital, operating room, outside hospital);

- Duration of invasive mechanical ventilation prior to enrollment (0 minutes; 1 to 360 minutes; >360 minutes);
- Chronic comorbidities (categories are not mutually exclusive)
 - Receipt of supplemental oxygen at place of residence prior to hospital admission (yes, no);
 - Coronary artery disease or heart failure with reduced ejection fraction (yes, no);
- Acute diagnoses at enrollment (categories are not mutually exclusive)
 - cardiac arrest (yes, no);
 - acute myocardial infarction (yes, no);
 - sepsis or septic shock (yes, no);

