The main analysis will be an intention-to-treat comparison of the primary outcome of VFDs between the higher, intermediate, and lower SpO₂ target groups among all patients enrolled in the trial except [1] those admitted during one of the 7-day washout periods and [2] those with a laboratory-confirmed diagnosis of COVID-19. Patients with a diagnosis of COVID-19 will be excluded from the main analysis for two reasons. First, the majority of the PILOT trial occurred prior the COVID-19 pandemic, with too few two-month study blocks occurring during the pandemic to ensure balance in the number of patients with COVID-19 between trial groups. Second, at the study hospital, ICU patients diagnosed with COVID-19 are transferred to a separate, dedicated COVID-19 ICU that was not participating in the PILOT trial. Thus, patients with COVID-19 are unlikely to have received significant exposure to the SpO₂ target intervention in the PILOT trial. Patients enrolled during washout periods and patients diagnosed with COVID-19 will be included in sensitivity analyses (see *Sensitivity Analyses* below).

It is possible to estimate a conditional effect, which is interpreted as the effect of a given SpO₂ target on an individual patient given the values of the covariates for that

patient, or a marginal effect, which is interpreted as the population effect of implementing a given SpO₂ target as a general policy [52]. Since an SpO₂ target intervention may be applied both at the patient level as an individual intervention and at the unit level as a general policy, both may be of interest.

To estimate the conditional effect, we will use a proportional odds model with independent covariates of group assignment (higher, intermediate, or lower SpO₂ target) and time [53,54]. Time (in days) will be treated as a continuous variable with values ranging from 1 (first day of enrollment) to 1,097 (final day of enrollment) and will be analyzed using restricted cubic splines with multiple knots to allow for non-linearity resulting from seasonality or secular trends. For the purposes of declaring a statistically significant difference between groups in the primary endpoint, we will consider the conditional effect from the proportional odds model and a two-sided P value of 0.05.

To estimate the marginal effect, we will use generalized estimating equations (GEE) with study period as the cluster and an independent variable for group assignment (higher, intermediate, or lower SpO₂ target).

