For both approaches, in addition to assessing for an overall group effect within the model, we will estimate the differences between each pair of SpO₂ targets by extracting 95% confidence intervals from the model.

Sensitivity Analyses of the Primary Outcome

- We will repeat the primary analysis using alternative statistical approaches to comparing the VFDs outcome between groups such as zero-inflated Poisson

regression or zero-inflated negative binomial regression, global rank scale analysis [55], and Fine and Gray competing risk regression.

- We will repeat the primary analysis with adjustment for pre-specified baseline covariates of age, sex, race and ethnicity, source of ICU admission, vasopressor receipt, and acute diagnoses at enrollment, and severity of illness as assessed by the non-respiratory SOFA score.
- We will repeat the primary analysis replacing the continuous covariate of time with a categorical covariate of season defined as: winter (January, February, March); spring (April, May, June); summer (July, August, September); and fall (October, November, December).
- We will repeat the primary analysis among all patients enrolled in the trial, including [1] patients initiated on invasive mechanical ventilation in a study location during one of the pre-specified 7-day washout periods and [2] patients with a diagnosis of COVID-19.

Analysis of Effect Modification for the Primary Outcome

We will examine whether pre-specified baseline variables modify the effect of study group on the primary outcome using formal tests of statistical interaction in a proportional odds model. Independent variables will include study group assignment, the potential effect modifier of interest, and the interaction between the two (e.g., study group * presence of sepsis or septic shock) and time. Significance will be determined by the P value for the interaction term, with values less than 0.10 considered to suggest a potential interaction and values less than 0.05 considered to confirm an interaction.

We will examine whether the following baseline variables modify the effect of study group on the primary outcome:

1. Age;
2. Race and ethnicity (Hispanic, Non-Hispanic Black, Non-Hispanic White, Other);
3. Source of admission to the ICU (ED, hospital ward, another ICU in the study hospital, operating room, outside hospital);
4. Duration of invasive mechanical ventilation prior to enrollment;
5. Chronic comorbidities (categories are not mutually exclusive)

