It is possible to estimate a conditional effect, which is interpreted as the effect of a given SpO₂ target on an individual patient given the values of the covariates for that patient, or a marginal effect, which is interpreted as the population effect of implementing a given SpO₂ target as a general policy.⁵² Since an SpO₂ target intervention may be applied both at the patient level as an individual intervention and at the unit level as a general policy, both may be of interest.

To estimate the conditional effect, we will use a proportional odds model with independent covariates of group assignment (higher, intermediate or lower SpO₂ target) and time.^{53 54} Time (in days) will be treated as a continuous variable with values ranging from 1 (first day of enrolment) to 1097 (final day of enrolment) and will be analysed using restricted cubic splines with multiple knots to allow for non-linearity resulting from seasonality or secular trends. For the purposes of declaring a statistically significant difference between groups in the primary endpoint, we will consider the conditional effect from the proportional odds model and a two-sided p value of 0.05.

To estimate the marginal effect, we will use generalised estimating equations with study period as the cluster and

an independent variable for group assignment (higher, intermediate or lower SpO₂ target).

For both approaches, in addition to assessing for an overall group effect within the model, we will estimate the differences between each pair of SpO₂ targets by extracting 95% CIs from the model.

Sensitivity analyses of the primary outcome

- ▶ We will repeat the primary analysis using alternative statistical approaches to comparing the VFDs outcome between groups such as zero-inflated Poisson regression or zero-inflated negative binomial regression, global rank scale analysis⁵⁵ and Fine and Gray competing risk regression.
- ▶ We will repeat the primary analysis with adjustment for prespecified baseline covariates of age, sex, race and ethnicity, source of ICU admission, vasopressor receipt, acute diagnoses at enrolment, and severity of illness as assessed by the non-respiratory SOFA score.
- ▶ We will repeat the primary analysis replacing the continuous covariate of time with a categorical covariate of season defined as: winter (January, February, March); spring (April, May, June); summer (July, August, September); and fall (October, November, December).

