3. Peak airway pressure
4. Receipt of mandatory ventilator mode
5. Number of arterial blood gasses
6. Hemoglobin
7. Red cell transfusion

21. Assessment of Compliance with the Assigned SpO₂ Target

All SpO₂ values measured during invasive mechanical ventilation are assessed for compliance with the assigned SpO₂ target. An SpO₂ value is considered compliant with the trial protocol if any of the following conditions are met:

1. Measured SpO₂ is within the target range
2. Measured SpO₂ is above the target range and the FiO₂ is 21%
3. Measured SpO₂ is below the target range and the FiO₂ is 100%
4. Measured SpO₂ occurs after treating clinicians have completed an SpO₂ target modification sheet

22. Interim Analysis

On March 23, 2020, the DSMB conducted a single, planned interim analysis for efficacy and safety at the anticipated halfway point of the trial. The interim analysis included data from patients enrolled during the first 18 months of the trial. According to the criteria specified in the trial protocol, the stopping boundary for efficacy would have been met if the P value for the difference between groups was <0.001 using a proportional odds model with independent covariates of group assignment (higher, intermediate, or lower SpO₂ target) and time. A stopping boundary for futility was not pre-specified. After conducting the planned interim analysis, the DSMB recommended the study continue without modification.

The DSMB reserves the right to stop the trial at any point, request additional data or interim analyses, or request modifications of the study protocol as required to protect patient safety.

Use of the conservative Haybittle-Peto boundary ($P < 0.001$) will allow the final analysis to be performed using an unchanged level of significance ($P = 0.05$).

23. Pre-specified Baseline Co-variates

We will repeat the primary analysis with adjustment for the following pre-specified baseline covariates: age (continuous), sex (male, female), race and ethnicity (Hispanic, Non-Hispanic Black, Non-Hispanic White, Other), source of ICU admission (ED, hospital ward, another ICU in the study hospital, operating room, outside hospital), vasopressor receipt (yes, no), and acute diagnoses at enrollment (cardiac arrest, acute myocardial infarction, sepsis or septic shock, acute respiratory distress syndrome), and severity of illness as assessed by the non-respiratory SOFA score.

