To account for non-linear relationships, continuous variables will be analyzed using restricted cubic splines with between 3 and 5 knots.

24. Corrections for Multiple Testing

We have pre-specified a single primary outcome and a single secondary outcome. Consistent with recommendations of the Food and Drug Administration [65] and the European Medicines Association [66], each will be tested using a two-sided p-value with a significance level of 0.05. For all other analyses, emphasis will be placed on the estimate of effect size with 95% confidence intervals, as recommended by the *International Committee of Medical Journal Editors* [67], and no corrections for multiple comparisons will be performed.

25. Handling of Missing Data

The primary outcome of VFDs is not anticipated to be missing for any patients.

Missing data will not be imputed for the primary outcome or any secondary or exploratory outcomes. None of the covariates pre-specified for the adjusted analysis are anticipated to be missing for any patients. In additional adjusted analyses, any missing data for covariates will be imputed using multiple imputations.

26. Rationale for Waiver of Informed Consent

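### The model that declares significance for ventilator-free days adjusts for no patient characteristic; the pre-specified baseline covariates serve only a sensitivity analysis, which gives up a modest amount of power

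*Combined protocol and SAP*

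**What the plan says.** The final protocol (version 4/7/2021), section 11.0, sets the primary analysis: "We will use a proportional odds model with independent covariates of group assignment" and time, with time entered as a restricted cubic spline. The SAP (Main Analysis of the Primary Outcome) and its published form use the same model: "To estimate the conditional effect, we will use a proportional odds model with independent covariates of group assignment" and time. For declaring significance, "we will consider the conditional effect from the proportional odds model and a two-sided P value of 0.05". The marginal GEE model in the same section has group only.

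Baseline adjustment appears under Sensitivity Analyses, in the protocol ("We will repeat the primary analysis with adjustment for pre-specified baseline covariates") and in the SAP ("We will repeat the primary analysis with adjustment for pre-specified baseline covariates of age, sex, race and ethnicity", followed by the rest of the list). The supplement, section 23, gives the full list with categories: age, sex, race and ethnicity, source of ICU admission, vasopressor receipt, four acute diagnoses and non-respiratory SOFA. It adds that "continuous variables will be analyzed using restricted cubic splines with between 3 and 5 knots". Section 25 of the supplement expects none of these covariates to be missing, and has multiple imputation as a fallback. The effect-modification models enter one baseline variable at a time with its interaction, so they are not an adjusted primary analysis.

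**The concern.** Covariates that predict VFDs make a test of the group effect more powerful at no cost in patients. Here the list is written, the data are collected and a missing-data rule exists, yet the list cannot affect the declared result.

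The SAP also describes the conditional effect as the effect for an individual patient at that patient's covariate values. In the decisive model the only covariate besides group is the day of enrollment, so no patient characteristic is conditioned on. At stake is a few points of power, not the validity of the comparison.

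**Working it through.** **Inputs.** From the SAP, Sample Size Estimation and Power Calculation: N 2,250, SD 11.4 days, difference 2.0 days, two-sided alpha 0.05, intra-cluster intra-period correlation (ICC) 0.01. From Randomization and Treatment Allocation: 18 periods. Hence 2,250/3 = 750 per group, 2,250/18 = 125 per period, 6 periods per group. Assumed, because the documents are silent: covariate R² of 0.10 to 0.25, all of it within periods.

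**1. The plan's figure.** SE = 11.4 × √(2/750) = 0.589 days; 2.0/0.589 = 3.40. A t-test on 1,498 df gives 92.4%, against the stated 92%. This is one pairwise comparison without covariates and without the ICC.

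**2. Same basis with adjustment.** Residual SD = 11.4 × √(1 − R²).

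**3. With the ICC.** Variance of a period mean, in SD² units: v = 0.01 + 0.99(1 − R²)/125. Pairwise SE = 11.4 × √(2v/6), tested on 18 − 3 = 15 df.

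| R² | Residual SD | Power, no ICC | v | Pairwise SE (days) | Power, ICC 0.01 |
|---|---|---|---|---|---|
| 0 | 11.40 | 92.4% | 0.01792 | 0.88 | 56.5% |
| 0.10 | 10.81 | 94.7% | 0.01713 | 0.86 | 58.4% |
| 0.20 | 10.20 | 96.7% | 0.01634 | 0.84 | 60.4% |
| 0.25 | 9.87 | 97.5% | 0.01594 | 0.83 | 61.5% |

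**4. Overall three-group test, period level.** With a 4-knot spline the denominator df are 18 − 1 − 2 − 3 = 12. For the assignment sequence in protocol section 4.0 and a 2.0-day benefit of the lower target, with knots at conventional quantiles (assumed), the noncentrality is 6.41 at R² 0 and scales by 0.01792/v to 6.71, 7.03 and 7.21. Noncentral F power is 50.2%, then 52.1%, 54.1% and 55.2%. With 5 knots (11 df) it is 46.7%, then 48.6%, 50.5% and 51.6%. A linear simulation (6,000 runs per setting) gave 49.5-50.1% rising to 52.0%, 54.9% and 54.3% with 4 knots, and 46.3-46.9% rising to 48.4%, 51.3% and 51.6% with 5. Type I error was 4.2-5.5%.

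**5. How the gain appears in a proportional odds model.** Simulation of 750 against 750, unclustered, VFD-like distribution, 600 runs (Monte Carlo error about 1 point):

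| Latent R² | Log odds ratio, unadjusted to adjusted | SE | Power |
|---|---|---|---|
| 0.10 | 0.309 to 0.331 | 0.091 to 0.092 | 91.8% to 96.2% |
| 0.20 | 0.311 to 0.359 | 0.091 to 0.092 | 91.3% to 96.3% |

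The standard error does not shrink; the adjusted log odds ratio moves away from zero.

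**6. Covariates without a period correction.** Ignoring period understates the variance by the factor k = 125v/[0.01 + 0.99(1 − R²)]. The 2-df chi-square critical value is 5.99 and its upper tail is exp(−x/2), so actual type I error is about exp(−2.996/k). For R² 0, 0.10, 0.20 and 0.25, k is 2.24, 2.38, 2.55 and 2.65, giving 26.3%, 28.3%, 30.8% and 32.3%. Simulation with the time spline gave 26.5-27.3%, 29%, 31% and 33%.

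**7. Which period correction.** With 2 and 12 df the F tail is (1 + F/6)^−6. A large-sample Wald test rejects when F > 2.996: 1.499^−6 = 8.8%. A likelihood-ratio test rejects when 18 ln(1 + F/6) > 5.99: exp(−6 × 0.333) = 13.6%. Only a small-sample reference distribution holds 5%.

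**The case against.** The current documents agree with one another, the adjusted analysis is pre-specified and will be reported, and leaving prognostic covariates out of a decisive test is a legitimate choice. The gain rests on an assumed R². At 0.10 it is about 2 points, and a second period-mean simulation (20,000 runs, 4 knots) gave less there: 50.7% to 51.4%, with 53.5% at 0.20 and 55.1% at 0.25. On unclustered inputs, the overall proportional odds test moves only from about 98% to 99.0% (R² 0.10) or 99.5% (0.20). The change also comes after an interim look.

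Much of this stands. It limits the point to efficiency, makes power the right word rather than a smaller standard error, and makes the change unsafe on its own. It does not show a reason for keeping a finished covariate list out of the decisive model.

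Three stronger readings are tempting and unsupported:
- A reader might infer that the group-plus-time test is biased or invalid without these covariates. Nothing in the documents shows that; the inflated error in step 6 comes from within-period correlation and is present with or without them.
- A reader might infer that adjustment would deal with that correlation, or bring power back to 92%. Steps 3 and 6 show that it does neither.
- A reader might treat the initial protocol's secondary VFD analysis, which had most of these covariates and a random study-period effect, as an abandoned commitment. That text is superseded, and adjustment was secondary there too.

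**Conclusion.** The point holds as a modest, inexpensive improvement. For R² of 0.10 to 0.25, adjustment adds about 2 to 5 points of power, whether on the plan's unclustered inputs or with ICC 0.01 and a period-level correction. The clustered figures assume equal periods of 125, a linear approximation, and covariates that explain none of the between-period variance. If they explained some of it the gain would be larger, but the documents give no basis for claiming that.

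**What to change.** Before any grouped results reach those who decide the change:

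- Put the supplement section 23 list into the decisive model with group and time, and keep group-plus-time as the sensitivity analysis.
- State one knot number for age and SOFA within the 3-to-5 range; a range is too open for a decisive model.
- Limit SOFA, vasopressor receipt and acute diagnoses to information at or before time zero. Supplement section 18 lists SOFA under Day 0, while titration begins within 15 minutes of ventilation. Vasopressors and diagnoses are defined at enrollment without a measurement window. Impute missing components with the multiple imputation already planned.
- Acute illnesses are collected manually only. Protocol section 7.2 states blinded collection for endpoints, not for these. ARDS or other manually collected diagnoses can be dropped if ascertainment is a concern, at some loss of R².
- Pair the change with a within-period correction using a small-sample reference: a period-level F test on about 12 df, or the random period effect named in DSMB charter section 10 with small-sample degrees of freedom. Fixed period effects are not available, because each period has one target.

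The cost is no new data and a short amendment. Downsides to state:

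- The odds ratio becomes conditional on more covariates.
- The final model will differ from the one reported for the March 2020 interim analysis, whose boundary "would have been met if the P value for the difference between groups was <0.001 using a proportional odds model" with group and time.
- The charter bars the principal investigator and enrolling or treating staff from grouped data (section 6). However, the study biostatistician prepares the DSMB reports (section 8), and the study statistician can unblind the board (section 6). The amendment should therefore record that it was decided by people without access to grouped data.

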 - acute respiratory distress syndrome (yes, no);
- Receipt of vasopressors at enrollment (yes, no);
- Non-respiratory SOFA score at enrollment (continuous variable);
- Time period (before the COVID-19 pandemic [July 2018 - December 2019], during the COVID-19 pandemic [January 2020 – August 2021]).

Analysis of the Secondary Outcome

The sole pre-specified secondary outcome of 28-day in-hospital mortality will be compared between the three study groups in an intention-to-treat fashion in the primary analysis population using a logistic regression model with independent covariates of group assignment (higher, intermediate, or lower SpO₂ target) and time. We also will perform pair-wise comparisons between the lower and intermediate groups, lower and higher groups, and intermediate and higher groups using the same statistical approach.

Analysis of the Exploratory Outcomes

Each of the exploratory outcomes will be compared between groups in an intention-to-treat fashion in the primary analysis population. Continuous outcomes will be compared between groups using a proportional odds model with independent covariates of group assignment (higher, intermediate, or lower SpO₂ target) and time. Categorical outcomes will be compared between groups using a logistic regression model with independent covariates of group assignment (higher, intermediate, or lower SpO₂ target) and time.

Corrections for multiple testing

We have pre-specified a single primary outcome and a single secondary outcome. Consistent with recommendations of the Food and Drug Administration and the European Medicines Association, each will be tested using a two-sided p-value with a significance level of 0.05. For all other analyses, emphasis will be placed on the estimate of effect size with 95% confidence intervals, as recommended by the

International Committee of Medical Journal Editors, and no corrections for multiple comparisons will be performed.

Handling of missing data

The primary outcome of VFDs is not anticipated to be missing for any patients. Missing data will not be imputed for the primary outcome or any secondary or exploratory outcomes. In adjusted analyses, missing data for covariates will be imputed using multiple imputations.

Interim Analysis

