- ▶ We will repeat the primary analysis among all patients enrolled in the trial, including¹ patients initiated on invasive mechanical ventilation in a study location during one of the prespecified 7-day washout periods and² patients with a diagnosis of COVID-19.

Analysis of effect modification for the primary outcome

We will examine whether prespecified baseline variables modify the effect of study group on the primary outcome using formal tests of statistical interaction in a proportional odds model. Independent variables will include study group assignment, the potential effect modifier of interest and the interaction between the two (eg, study group \times presence of sepsis or septic shock) and time. Significance will be determined by the p value for the interaction term, with values <0.10 considered to suggest a potential interaction and values <0.05 considered to confirm an interaction.

We will examine whether the following baseline variables modify the effect of study group on the primary outcome:

1. Age;
2. Race and ethnicity (Hispanic, non-Hispanic Black, non-Hispanic white, Other);
3. Source of admission to the ICU (ED, hospital ward, another ICU in the study hospital, operating room, outside hospital);
4. Duration of invasive mechanical ventilation prior to enrollment;
5. Chronic comorbidities (categories are not mutually exclusive)
 - i. Receipt of supplemental oxygen at place of residence prior to hospital admission (yes, no);

- ii. Coronary artery disease or heart failure with reduced ejection fraction (yes, no);
- 6. Acute diagnoses at enrollment (categories are not mutually exclusive)⁵⁶
 - i. cardiac arrest (yes, no);
 - ii. acute myocardial infarction (yes, no);
 - iii. sepsis or septic shock (yes, no);
 - iv. acute respiratory distress syndrome (yes, no);
- 7. Receipt of vasopressors at enrollment (yes, no);
- 8. Non-respiratory SOFA score at enrollment;
- 9. Time period before the COVID-19 pandemic (July 2018 to December 2019), and during the COVID-19 pandemic (January 2020 to August 2021).

Analysis of the secondary outcome

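### P<0.05 on any one of 13 uncorrected interaction tests counts as confirming effect modification; with no true heterogeneity, the chance of at least one false confirmation is 49% if the tests are independent and lower if they are correlated

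*Combined protocol and SAP*

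**What the plan says.** The rule "values less than 0.10 considered to suggest a potential interaction and values less than 0.05 considered to confirm an interaction" stands in the SAP, under Analysis of Effect Modification for the Primary Outcome, and in the protocol dated 4/7/2021, section 11.0. The published article has it in nearly the same words ("values <0.05 considered to confirm an interaction").

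Each modifier gets its own proportional odds model with group, that modifier, their interaction and time. The list has nine headings. Chronic comorbidities contains two separate yes/no items and acute diagnoses contains four, so 13 modifiers are tested: age, race and ethnicity, admission source, prior ventilation, home oxygen, coronary disease or heart failure, cardiac arrest, myocardial infarction, sepsis, ARDS, vasopressors, non-respiratory SOFA score and time period.

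Protocol section 11.0 (Corrections for multiple testing) tests the primary outcome and the one secondary outcome at 0.05 each. For everything else, "no corrections for multiple comparisons will be performed". Supplement section 24 repeats this and says that for those analyses "emphasis will be placed on the estimate of effect size with 95% confidence intervals". The current effect-modification text does not itself call these tests exploratory.

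**The concern.** An uncorrected set of interaction tests is normal when the results are offered as leads for later work. Here the plan fixes in advance that one P value below 0.05 settles the matter. A subgroup finding that arises by chance could then be reported as confirmed under a pre-specified rule, and cited as evidence that, for example, patients with sepsis or cardiac arrest respond differently to the oxygen target.

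For time period there is a second route to a false result. Both the group and the period are properties of a two-month block, so ordinary variation between blocks can look like an interaction.

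**Working it through.** **The plan's own figure.** The documents state no error rate for the set of interaction tests, so there is none to reproduce. The one stated design figure, 92% power, is not an input here. It does reproduce for two groups of 750 (2,250/3), a difference of 2.0 days and SD 11.4: SE = 11.4 × √(2/750) = 0.589; 2.0/0.589 − 1.96 = 1.44; power 92.5%.

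**Independent tests, no true interaction, each test at its nominal level.**
- At least one P<0.05 among 13: 1 − 0.95^13 = 0.487.
- At least one P<0.10 among 13: 1 − 0.90^13 = 0.746.
- Leaving out time period: 1 − 0.95^12 = 0.460. The result does not rest on that modifier.

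**Correlated tests.** The documents give no correlation between the tests, so the values below are assumptions. With three groups, an interaction has 2 × (levels − 1) degrees of freedom: race and ethnicity 6, admission source 8, prior ventilation 4 (the protocol's three categories), yes/no modifiers 2, and age and SOFA 2 each if linear. Simulating 100,000 sets of 13 equally correlated chi-square tests gives:

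| Assumed correlation | At least one P<0.05 | At least one P<0.10 |
|---|---|---|
| 0 | 48.5% | 74.4% |
| 0.2 | 46.1% | 71.3% |
| 0.4 | 40.2% | 63.7% |
| 0.7 | 28.1% | 46.5% |

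The results at 0.4 and 0.7 depend somewhat on the degrees of freedom. Supplement section 23 says "continuous variables will be analyzed using restricted cubic splines with between 3 and 5 knots", but that is written for the covariate-adjusted analysis and its reach to the interactions is unclear. With five-knot splines for age and SOFA the P<0.05 figures become 40.7% and 29.2%. If every test had a single degree of freedom, a simplification for three groups, they would be 37.8% and 24.1%. Hence about 38 to 41% at 0.4 and 24 to 29% at 0.7.

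**Time period.** Inputs: the block sequence in protocol section 4.0; 18 blocks of 125 patients (2,250/18); the first nine blocks pre-pandemic (July 2018 to December 2019); days 1 to 1,097 with the last 7 days of each block empty; SD 11.4. There is no true interaction. The model is linear with a calendar-time spline (3, 5 or 7 knots) and no block term, with 3,000 runs per setting. Rejection rate at nominal 5%:

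| Between-block correlation left after the spline | 3 / 5 / 7 knots |
|---|---|
| 0 | 5.8 / 5.3 / 4.9% |
| 0.0025 | 11.0 / 10.7 / 10.1% |
| 0.005 | 16.1 / 15.9 / 15.0% |
| 0.01 | 27.0 / 24.7 / 27.2% |

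A proportional odds version (1,500 runs; outcome shape assumed so as to match a median of 22 and an IQR of 0 to 25) gave about 5% at 0, 17 to 18% at 0.005 and 28 to 29% at 0.01.

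An F test on the 18 block means with group, period, spline and their interaction has 13 minus the number of knots residual degrees of freedom, so 10, 8 or 6. It held 4.3 to 5.4% in all settings.

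**The case against.** The rule is worded per modifier, and nowhere does the plan claim to control error over the set; it says openly that it does not. On that view the 49% only puts a number on a disclosed choice, under the extreme case of no interaction at all. This stands as far as the missing correction goes: it is no fault in itself. It does not justify the word confirm, which promises more than one uncorrected P value can deliver.

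A reader might infer that the rule contradicts the statement on multiple testing. The documents do not support that. The statement sets an emphasis on estimates and intervals; it does not forbid P values or thresholds. Both could be followed at once, so this is a tension.

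The list is not a blind search. Subgroup evaluation is a stated secondary aim, and the initial protocol gave expected directions for at least eight of these modifiers. That table is superseded, however, and the current tests do not use direction.

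On time period, the inflation depends wholly on an unknown. The 0.01 in the sample-size section comes from a prior trial and is not described as net of a time spline. At zero residual correlation the test is sound. A reader might also infer that the same argument condemns the primary model, which has no block term either. That is a separate question and is not shown here.

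**Conclusion.** The rule should be changed as written. It lets a single P<0.05 among 13 uncorrected tests be called confirmation. With no true heterogeneity, the chance of at least one false confirmation is 49% under independence, and lower under correlation: about 38 to 41% at 0.4 and 24 to 29% at 0.7. Those two correlations are assumed. Even the lowest of these figures is close to one in four.

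The time-period point is secondary and conditional: about 5% if no between-block correlation remains, 15 to 16% at 0.005 and 25 to 27% at 0.01 in the linear model. It would be wrong to read 25 to 27% as the actual error rate, because the residual correlation is unknown and 0.01 is only the upper end shown. The other 12 modifiers vary between patients within a block, so this point does not extend to them.

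Nor does any of this weaken the primary or secondary outcome tests. The rule does not enter them.

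**What to change.** Replace the threshold sentence in the SAP, in protocol section 11.0 and, by a dated note, in the published article with:

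> Thirteen pre-specified modifiers will be examined. These analyses are exploratory and not adjusted for multiplicity. For each modifier other than time period, effect estimates with 95% CIs (by category, or at pre-specified values or as a curve for age and non-respiratory SOFA score) and the interaction P value will be reported. For time period, estimates by period will be reported descriptively, without an interaction P value or patient-level confidence interval. No interaction will be described as confirmed.

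If a time-period test is wanted, use a block-level test with residual degrees of freedom based on the 18 blocks, such as the F test on block means. State that it works on mean ventilator-free days, not on the odds-ratio scale, and that its power is low. For a 2-day interaction, power is 12 to 15% at a residual correlation of 0.01, 15 to 20% at 0.005 and 21 to 29% at 0, so descriptive reporting gives up little. A random intercept with an uncorrected Wald test is not a substitute: at 0.01 it still rejected in 19 to 25% of runs (maximum likelihood) or 8 to 10% (REML).

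The cost is one sentence in three places and one changed method for one modifier, with no new data. The last patient was enrolled on August 31, 2021 and the article is published, so the change would come late and should be dated as such. The real price is that no subgroup effect can be called confirmed from this trial alone.
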